8.3.4.1 Characteristics of Infusion Related Reactions and Pulmonary Toxicities

Symptoms associated with AESIs will be summarized using counts and percentages. Multiple occurrences of the same symptom within a subject will be summarized only once for the time frame under consideration.

Additional summaries to characterize IRRs will include summary statistics of the time from the most recent zanidatamab exposure to the first subsequent IRR (for all infusions during which IRRs occur); percent of subjects with a history of any risk factor for IRRs including atopy, hypersensitivity, anaphylaxis, and/or allergy; the percent of subjects who underwent a tryptase test (and the proportion who had elevated tryptase levels); a frequency distribution of IRR onset by treatment cycle, and a frequency distribution of treatments (if any) provided for the IRRs.

Additional summaries to characterize non-infectious pulmonary toxicities will include the proportion of subjects with symptoms; a frequency distribution of symptoms; the proportion of subjects with a history of risk factors for non-infectious pulmonary toxicity, and a frequency distribution of risk factors.

8.3.4.2 Characteristics Confirmed Cardiac Events

Additional summaries to characterize confirmed cardiac events are data driven and may include summaries of the proportion of subjects with symptoms; the proportion of subjects with limitations to physical activity (most severe if a subject has multiple limitation events); and the proportion of subjects with any elevated brain natriuretic peptide (BNP) or troponins and elevation status.

8.3.5 Clinical Laboratory Results

Per protocol, samples for hematology, serum chemistry, and urinalysis will be collected at the following timepoints: Screening visit, day 1 of each cycle, EOT visit and at the 30-day post last dose visit. Samples for coagulation will be collected at the screening visit, and at day 1 of cycle 1. All laboratory results will be converted into Système International (SI) units for analysis and graded using the laboratory reference ranges from individual laboratories and the criteria from NCI CTCAE (Common Terminology Criteria for Adverse Events, Version 5) by the Sponsor. If one or more normal ranges for a laboratory are missing, then a standard normal range from the Merck Manual will be used to perform toxicity grading.

8.3.5.1 Laboratory Results

Listings of select laboratory results will be produced for all subjects by nominal visit and where appropriate, may include the change from baseline, laboratory toxicity grade, and reference range. Each abnormal value will be flagged to show whether it is a value below or above the reference range. Laboratory abnormalities will be summarized in a table using counts and percentages.

8.3.5.2 Laboratory Toxicities

Laboratory toxicities by grade will be summarized using counts and percentages. For each graded laboratory test, only the worst (i.e., highest) toxicity grade will be counted for subjects with multiple toxicities within a time period (including scheduled and unscheduled assessments). For each graded laboratory test, shift tables will be produced to summarize the shift in toxicity grade from baseline to the worst treatment-emergent grade. In addition to summary tables, listings of laboratory test results may be provided for subjects with any Grade 3 or higher toxicities.

Table 8: Toxicity Terms for Laboratory Parameters Graded for both High and Low values

Analyte	Term (high values)	Term (low values)
Calcium	Calcium high	Calcium low
Blood glucose	Blood glucose high	Blood glucose low
Potassium	Potassium high	Potassium low
Sodium	Sodium high	Sodium low
Hemoglobin	Hemoglobin high	Hemoglobin low
Lymphocyte Count	Lymphocyte count high	Lymphocyte count low

Magnesium	Magnesium high	Magnesium low
Phosphorous	Phosphorous high	Phosphorous low
WBC	White blood cell count high	White blood cell low

8.3.6 Cardiac Function

8.3.6.1 Left Ventricular Ejection Fraction

The following left ventricular ejection fraction (LVEF) endpoints will be summarized using counts and percentages.

- LVEF result at baseline (<50%, ≥ 50%)
- Minimum LVEF result post-baseline (<50%, ≥ 50%)
- Minimum post-baseline LVEF result with a decrease of ≥10 percentage points or more from the baseline result
- Post-baseline LVEF result that is < 50% with a decrease of ≥10% or more from the baseline result

In addition, a shift table based on the <50% and ≥50% cut-offs will be used to summarize changes of the baseline LVEF values against the lowest treatment-emergent values.

8.3.6.2 ECG

ECG interpretations (e.g., normal, or abnormal) will be summarized using counts and percentages. For abnormal ECG, the frequency of clinically significant findings will also be summarized using counts and percentages. The following QTcF interval endpoints will be summarized using counts and percentages:

- QTcF interval increase from baseline (<30 milliseconds, 30–60 milliseconds, and >60 milliseconds) during the treatment period.
- QTcF interval prolongation <450 msec, 450-480 msec, >480 msec during the treatment period

For both endpoints, the worst value for each subject during the treatment period (first dose date through the end of the safety reporting period, i.e. 30 days after the last dose of study treatment) will be summarized.

8.3.7 Vital Signs

Vital signs (blood pressure, heart rate, respiratory rate, and temperature) will be summarized using descriptive statistics (i.e., mean, median, standard deviation, and range).

8.3.8 ECOG Performance Status

ECOG performance status over time will be listed by subject. The baseline status, best status post-baseline, worst status post-baseline, and status at end of treatment will be summarized using counts and percentages.

8.3.9 Post-Study Treatment Systemic Anti-Cancer Therapies

Post-study treatment systemic anti-cancer therapies (i.e., subsequent treatment) will be coded using the World Health Organization Drug Dictionary (WHO-DD) summarized by preferred term using counts and percentages. Multiple occurrences of the same therapy within a subject will be summarized only once.

8.4 Quality of Life, Disease-Related Pain Analyses and Opioid Use

Analysis of Quality-of-life endpoints will be based on the safety analysis set for cohort 1 and cohort 2 separately.

CCI

[REDACTED]

[REDACTED]

[REDACTED]

[REDACTED]

[REDACTED]

[REDACTED]

[REDACTED]

[REDACTED]

[REDACTED]

[REDACTED]

[REDACTED]

CCI [Redacted]

[Redacted]

[Redacted]

[Redacted]

[Redacted]

[Redacted]

[Redacted]

[Redacted]

[Redacted]

[Redacted]

[Redacted]

[Redacted]

[Redacted]

8.5 Immunogenicity Analyses

All immunogenicity analyses will be based on the immunogenicity analysis set described in [Section 7.1](#).

Subjects developing an anti-drug antibody response will be listed. Subjects ‘positive’ in Tier 1 and Tier 2 will be listed along with their Tier 3 titers. If available, domain specificity data and anti-ZW25 neutralizing antibodies will be listed and summarized as well.

The occurrence of anti-drug antibodies (ADAs) will be summarized using counts and percentages by nominal time point and by cohort. Titers for confirmed positive ADA will be summarized using descriptive statistics (e.g., n, geometric mean, geometric coefficient of variance). When determining post-baseline incidence, patients are considered to be ADA positive if they are initially ADA negative at baseline and test positive for ADAs following study drug exposure (“treatment-induced ADA response”), or if they are ADA positive at baseline and the titer of one or more post-baseline samples is at least 4-fold greater than the titer of the baseline sample (“treatment-enhanced ADA response”). Patients are considered to be ADA negative if they are ADA negative and all post-baseline samples are negative, or if they are ADA positive at baseline but do not have any post-baseline samples with a titer that is at least 4-fold greater than the titer of the baseline sample (“treatment unaffected”). Duration of antibody response is also monitored and identified as either “transient” (ADA positive result detected at only one post-baseline sampling timepoint [excluding last timepoint] or at 2 or more timepoints during treatment or safety follow-up where the first and last ADA positive samples are separated by a period of <16 weeks, irrespective of any negative samples in between) or “persistent” (ADA positive result detected at the last post-baseline sampling timepoint or at 2 or more timepoints during treatment or safety follow-up where the first and last ADA positive samples are separated by a period \geq 16 weeks, irrespective of any negative samples in between).

Additional analyses to evaluate the association between development of ADAs and efficacy/adverse events may also be performed based on treatment-emergent ADA results.

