6.2 Study Objectives and Endpoints

Objectives	Endpoints

Primary:
 
 To evaluate the anti-tumor activity of zanidatamab monotherapy in subjects with advanced or metastatic HER2-amplified biliary tract cancers (BTC) 	
 Confirmed objective response rate (ORR) by the Response Evaluation Criteria in Solid Tumors version 1.1 (RECIST 1.1), assessed by independent central review (ICR)

Objectives	Endpoints

Secondary:
 
 To further evaluate the anti-tumor activity of zanidatamab monotherapy in subjects with advanced or metastatic HER2-amplified BTC To evaluate the safety and tolerability of zanidatamab monotherapy in subjects with advanced or metastatic HER2-amplified BTC 	
 Duration of response (DOR) by RECIST 1.1 assessed by ICR. Proportion of subjects with a DOR \geq16 weeks by RECIST 1.1 assessed by ICR. Disease control rate (DCR) by RECIST 1.1 assessed by ICR. Progression-free survival (PFS) by RECIST 1.1 assessed by ICR. ORR by RECIST 1.1 assessed by investigator. DOR by RECIST 1.1 assessed by investigator. Proportion of subjects with a DOR \geq16 weeks by RECIST 1.1 assessed by investigator. DCR by RECIST 1.1 assessed by investigator. PFS by RECIST 1.1 assessed by investigator. Overall survival (OS) Frequency and severity of adverse events (AEs) Frequency of serious adverse events (SAEs) and deaths Frequency and severity of clinical laboratory abnormalities Frequency of dose modifications of zanidatamab

Objectives	Endpoints

 • To evaluate the pharmacokinetics (PK) of zanidatamab • To evaluate the immunogenicity of zanidatamab 	
 • Serum concentrations of zanidatamab as a function of time post-dosing • PK parameters for single (first) dose and multiple doses • Population pharmacokinetics and exposure-response analyses. To be conducted according to the data analysis plan entitled “Population Pharmacokinetic and Exposure-Response Analysis to Support Regulatory Biologics License Application Submission of Study ZWI- ZW25- 203 in Biliary Tract Cancer” • Frequency, duration, and time of onset of anti-drug antibodies (ADA) and neutralizing antibodies, if applicable

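### SAP 8.5 counts any positive ADA sample toward duration, so in a treatment-enhanced subject background antibody below the 4-fold threshold can turn a brief boost into a persistent response

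*SAP*

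**What the plan says.** SAP 6.2 lists as a secondary endpoint "Frequency, duration, and time of onset of anti-drug antibodies (ADA) and neutralizing antibodies, if applicable". Protocol Section 2 lists the same endpoint.

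For frequency, SAP 8.5 gives a rule for each subject: "When determining post-baseline incidence, patients are considered to be ADA positive if they are initially ADA negative at baseline" and later test positive (treatment-induced), or if they are positive at baseline and "the titer of one or more post-baseline samples is at least 4-fold greater than the titer of the baseline sample" (treatment-enhanced). A baseline-positive subject is ADA negative, labelled treatment unaffected, if they "do not have any post-baseline samples with a titer that is at least 4-fold greater than the titer of the baseline sample".

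The same paragraph then turns to duration: "Duration of antibody response is also monitored and identified as either" transient or persistent.
- Transient is "ADA positive result detected at only one post-baseline sampling timepoint", the last timepoint excepted, or two or more positives with less than 16 weeks between first and last.
- Persistent is "ADA positive result detected at the last post-baseline sampling timepoint or at 2 or more timepoints during treatment or safety follow-up", where for the second limb the first and last positives are at least 16 weeks apart.

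Neither class mentions titer, baseline status or treatment-emergent status.

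**The concern.** The paragraph works with two meanings of positive. For incidence, antibody present before treatment is discounted unless the titer rises at least 4-fold. For duration, every positive sample counts, including those that show only the pre-existing antibody.

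In a treatment-enhanced subject, the response to zanidatamab is the rise. If the titer falls back to its baseline level and stays detectable, the rise is over, but samples remain positive and the duration rule keeps counting them. The label then describes how long the background antibody lasts, although the endpoint concerns the immunogenicity of zanidatamab. A reader would take persistent to mean a lasting response to the drug.

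**Working it through.** The documents give no ADA rate, prevalence or sample size, so there is no stated figure to reproduce. The check applies both rules of SAP 8.5, as written, to the same titer series.

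**Inputs from the documents**
- Sampling (Protocol Table 1): Cycle 1 Day 15, Cycle 2 Days 1 and 15, then Day 1 of Cycles 4, 6, 8, 10 and 12. With 28-day cycles these are weeks 2, 4, 6, 12, 20, 28, 36 and 44. Later cycles and the end-of-treatment and safety follow-up samples are left out for simplicity.
- Assay flow (Protocol 7.5): screening, confirmation, then a titer on confirmed positives, with no comparison with baseline.
- Population (SAP 7.1, Table 4): the immunogenicity set requires a baseline ADA result but does not exclude baseline-positive subjects.

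**Assumed:** the titers. Baseline-positive subjects start at 10, so the 4-fold threshold is 4 × 10 = 40.

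| Series | Incidence class | Duration as written | Duration counting only samples ≥ 40 if baseline positive |
|---|---|---|---|
| A. Baseline positive, 40 at week 6, 10 at all other visits | Enhanced | Persistent | Transient |
| B. Baseline positive, 20 throughout | Unaffected | Persistent, if classified | None |
| C. Baseline positive, 10 throughout | Unaffected | Persistent, if classified | None |
| D. Baseline positive, 10 to week 20, then negative | Unaffected | Persistent, if classified (20 − 2 = 18 weeks) | None |
| E. Baseline positive, 10 to week 6, then negative | Unaffected | Transient, if classified (6 − 2 = 4 weeks) | None |
| F. Baseline negative, positive at week 6 only | Induced | Transient | Transient |

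Series A is the point. The last sample is positive and the span is 44 − 2 = 42 weeks, so both limbs of persistent are met. Only the week 6 sample reaches 40. Counting that sample alone gives one timepoint, not the last, which is transient.

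**Direction in treatment-enhanced subjects.** Samples at 4-fold or more are a subset of all positive samples. Adding the rest can only move the first positive earlier, move the last positive later, or make the final sample positive. If the persistent criterion is met on the 4-fold samples, it is still met on all positives. The reverse does not hold, as series A shows.

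**Size, by illustration only.** Suppose 5 treatment-induced subjects, 2 of them persistent, and 1 treatment-enhanced subject like series A. The 4-fold count gives 2/6 = 33% persistent, and the rule as written gives 3/6 = 50%. Now add 4 treatment-unaffected subjects and suppose they are classified too. The result is 7/10 = 70% if their antibody stays detectable, or 3/10 = 30% if it clears by week 6.

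**The case against.** There are four fair objections.

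**The incidence rule classifies subjects, not samples.** In series A it makes the subject treatment-enhanced and is silent on the later samples. This stands. A reader might infer that the SAP itself calls those samples unaffected, and hence that transient is the answer its own rule gives. The documents do not say so. Counting by sample is a proposed convention, justified by what the endpoint is meant to describe.

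**The wording may already exclude treatment-unaffected subjects.** SAP 8.5 attaches the word response to the treatment-induced and treatment-enhanced classes only, and the duration sentence opens with antibody response. This is a reasonable reading, and on it series B to E receive no duration class. It is not stated, however: treatment-emergent status is named only for the optional analyses relating ADA to efficacy and adverse events. Nor does this reading help series A.

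**The bias is not one-way in general.** If treatment-unaffected subjects are classified, early clearance yields transient labels, and the 30% in the illustration lies below 33%. This stands. The one-way result is limited to treatment-enhanced subjects.

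**The consequence is small.** SAP 8.5 promises no persistent percentage, and Protocol 9.4.8 makes a summary of duration optional. No hypothesis is tested, and confirmed positives are listed with their titers, so a reader of the listings could tell a boost from background. This limits the weight of the point but does not correct the label.

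**Conclusion.** The point holds in a narrow form. As written, the duration rule lets positives below 4-fold count in a treatment-enhanced subject, and it can turn a brief boost into a persistent response. Nothing in Protocol 7.5, Protocol 9.4.8, SAP 7.1 or SAP Section 9 repairs this. Whether treatment-unaffected subjects receive a duration class is left to inference.

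Two stronger conclusions are tempting and not supported. One is that pre-existing antibody in baseline-positive subjects is in general labelled persistent. That requires classifying subjects whom the wording may already exclude, and antibody that clears early would be transient. The other is that the persistent share is inflated by a known amount. The 33% and 50% come from an invented split in which one subject changes label.

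Those affected under the narrow form are baseline positive, boosted at least 4-fold, and then back below 4-fold but still detectable. Baseline prevalence is not given. If 1 to 10 of about 100 subjects were baseline positive (an assumption), the number affected would lie between 0 and 10. The endpoint is a descriptive secondary one, and the primary ORR analysis is unaffected. The change is worth making because a stated rule gives a misleading label for a listed endpoint and the correction is cheap.

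**What to change.** Add to SAP 8.5: *Duration is classified only for treatment-induced and treatment-enhanced ADA responses; for subjects ADA positive at baseline, a post-baseline sample counts as positive for the transient/persistent classification only if its titer is at least 4-fold the baseline titer.*

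The cost is that sentence and one derivation flag. No new data are needed, because Tier 3 titers are already measured on confirmed positives. The persistent count may become smaller. A matching rule for time of onset, or a separate table row for pre-existing antibody, would be optional and is not needed to correct this defect.

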8.6 Pharmacokinetic Analyses

All pharmacokinetic (PK) analyses will be performed on the Pharmacokinetics analysis set defined in [Section 7.1](#). Pharmacokinetic sampling will be performed according to two different schedules. [Table 9](#) presents the PK sampling timepoints for both extensive and sparse sampling.

Table 9: PK Sampling time points for Zanidatamab

Cycle number / Cycle length	Day	Time Point	Time window	Extensive	Sparse
1 / 28 days	1	Pre-dose		X	X

		End of ZW25 infusion	+15 min	X	X
		2 hours post-dose	± 15 min	X	
		4 hours post-dose	± 15 min	X	
		8 hours post-dose	± 3 h	X	
	2	24 hours post-dose	±4 h	X	
	5	96 hours post-dose	±4 h	X	
	15	Pre-dose	- 4 h	X	X
		End of ZW25 infusion	+15 min	X	X
Cycle 2 / 28 days	1 and 15	Pre-dose	- 4 h	X	X
		End of ZW25 infusion	+15 min	X	X
Additional Even-Numbered Cycles ^a	1	Pre-dose	- 4 h	X	X
		End of ZW25 infusion	+15 min	X	X
EOT	-	-		X ^b	X ^b

EOT = end of treatment; h = hour; min = minute; PK = pharmacokinetics; ZW25=Zanidatamab.

Extensive sampling will be performed for the first 6 enrolled subjects only.

a Day 1 of Cycles 4, 6, 8, 10, and 12.

b Only required if subject has completed less than 6 months of treatment.

Table 10: Steady-State Extensive Pharmacokinetic Sampling Schedule on Cycle 4 or any Subsequent Cycle

Day	Time Point	Time window
1	Pre-dose	
	End of zanidatamab infusion	+15 min
	2 hours post-dose	± 15 min
	4 hours post-dose	± 30 min
	8 hours post-dose	± 3 hours
3	48 hours post-dose	± 1 days
5	96 hours post-dose	± 1 days

15	336 hours post-dose	± 3days
----	---------------------	---------

Extensive sampling at steady state: Performed for the first 10 suitable subjects in China who reach Cycle 4 and the first 20 suitable subjects in the rest of world who reach Cycle 4

8.6.1 Serum Concentrations

Peak and trough serum concentrations of zanidatamab will be summarized using descriptive statistics (e.g., n, mean, coefficient of variance) by nominal collection timepoint. Tabulations and graphs such as individual plots and mean plots may be presented.

8.6.2 Pharmacokinetic Parameters

Serum concentrations of zanidatamab will be measured as a function of time post-dosing.

For the extensive PK analysis set (dose 1 and steady-state), serum concentration-time data of each patient will be tabulated and graphically presented on linear and semilogarithmic scales. Pharmacokinetic parameters will be determined using standard noncompartmental method with actual collection time.

For each subject, the parameters listed below will be reported when there is sufficient data available to support the accurate estimation of the parameter based on actual sample collection times.

The following PK parameters will be derived for single (first) dose using extensive PK sampling data after dose 1:

- AUC_{last} area under the serum concentration-time curve from zero to the last measurable concentration for dose 1
- $AUC_{tau,1}$ area under the serum concentration-time curve tau (the time from the start to the end of the dosing interval) for dose 1
- AUC_{INF} area under the serum concentration-time curve from zero to infinity for dose 1
- $C_{max,1}$ maximum observed serum concentration for dose 1
- $C_{trough,1}$ trough serum concentration for dose 1
- $t_{1/2}$ terminal half-life for dose 1
- CL serum clearance for dose 1
- V_z volume of distribution in the terminal phase for dose 1

The following PK parameters will be reported for extensive subjects with multiple dosing at steady-state using PK sampling data:

- $AUC_{\tau,ss}$ area under the serum concentration-time curve tau (the time from the start to the end of the dosing interval) at steady-state
- $C_{max,ss}$ maximum observed serum concentration at steady-state
- $C_{trough,ss}$ trough serum concentration at steady-state
- $C_{ave,ss}$ average concentration over the dosing interval, calculated as AUC_{τ}/τ . Where tau is the dosing interval for Dose 1, at steady-state
- $t_{1/2,ss}$ terminal half-life at steady-state
- V_{ss} volume of distribution at steady-state
- Accumulation index for AUC_{τ} and C_{max} steady-state PK parameter value divided by the PK parameter value from dose 1
- Peak-to-trough ratio: C_{max}/C_{trough}

The following parameters will be derived and summarized for all subjects with either extensive or sparse sampling data:

- $R_{C_{trough}}$ accumulation index, calculated as C_{trough} (last dose)/ C_{trough} (first dose)
- $C_{trough,ss}$ trough concentration at steady state

PK parameters will be summarized using summary statistics (e.g., n, geometric mean, geometric coefficient of variance) by nominal timepoint.

CCI

[REDACTED]

[REDACTED]

[REDACTED]

